12.3 Safety Analysis

Adverse event rates will be summarized in all patients who received AGS-003. These rates will be described as the proportion of patients with the event, by grade, and supported with exact 95% confidence intervals.

12.4 Stopping Rule:

If during the trial 4 or more patients experience the undesirable event defined as unexpected bleeding or more difficult than usual perinephric dissection, accrual will be halted and the treatment will be deemed unsafe. Otherwise the accrual will continue for a total of 10 patients. The probability of excising the stopping rule within this study is a function of the true unknown probability of the event corresponding to the study population. The table below contains the probability of observing at least 4 undesirable events in the 10 patients for a variety of values of the true probability within the population.

True probability of undesirable event	0.2	0.3	0.4	0.5
Probability of exercising the stopping rule	0.12	0.35	0.62	0.83

The calculations above are based on the assumption that our study sample may be treated as a random sample from the population of interest.

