1.6 AGS-003 Safety

Previous clinical studies have demonstrated that single-agent AGS-003 and its predecessor product MB-002 are safe and well-tolerated. With more than 500 doses delivered across these studies, most drug-related adverse events (AEs) have been mild to moderate injection site reactions, with no reports of any drug-related AEs with Grade 3 or Grade 4 toxicity, and no drug-related serious adverse events (SAEs). No subjects in any studies of AGS-003 or MB-002 have developed autoimmune disease, and periodic assessments of autoimmunity markers in these studies have yielded no clinically significant findings. Of note, in all RCC studies each subject received AGS-003 manufactured from the subject's tumor (primary or metastatic RCC site), yet no subjects developed autoimmune reactions against their remaining (healthy) kidney.

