10.5 Adverse Events

10.5.1 Definition

An adverse event or adverse experience (AE) is any untoward medical occurrence associated with the use of a drug in humans, whether or not considered drug related. Therefore, an AE can be ANY unfavorable and unintended sign (including an abnormal laboratory finding, if clinically significant), symptom, or disease temporally associated with the use of a medicinal (investigational) product, whether or not considered related to the medicinal (investigational) product (attribution of ‘unrelated’, ‘unlikely’, ‘probable’, or ‘definite’).

An AE is considered “unexpected” if it is not listed in the investigator brochure or is not listed at the specificity or severity that has been observed; or if an investigator brochure is not required or available, is not consistent with the risk information described in the general investigational plan in other study-related documents.

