10.7 Reporting Adverse Events

Table 2. Guidelines for Routine Adverse Event Reporting for Pilot Studies (Regardless of Expectedness)

Attribution	Grade 1	Grade 2	Grade 3	Grade 4
Unrelated			X	X
Unlikely			X	X
Possible	X	X	X	X
Probable	X	X	X	X
Definite	X	X	X	X

All routine AEs occurring between the start of intervention until 30 days after the last intervention or until the event has resolved, the study patient is lost to follow-up, the start of a new treatment, or until the study investigator assesses the event(s) as stable or reversible, will be reported. New information will be reported when it is received.

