12.1 Sample Size Determination

A maximum of 10 patients will be enrolled in this study. In previous experiments, immune marker expression measurements varied widely, with means between 8.0 and 1,200; the coefficient of variation has been between 0.5 and 1.0 depending on the marker, method of measurement and disease setting. For power calculations, the possible effect of immunotherapy delivery model of expression has been ignored, and the (original scale) expressions are assumed to have mean (standard deviation) of 100 (75), and within-patient correlation = 0.50. If the measurements are log-normally distributed, the log-transformed outcome would have mean (standard deviation) of about 4.38 (0.68).

Comparing measurements at two time points, the within-patient effect of immunotherapy on an immune marker can be assessed using a permutation paired t-test. A paired t-test with a two-sided significance threshold of 0.05 has 80% power to detect a mean of at least 5.08 in the post-measurements, if the pre-measurements are as described above: a 20% increase in the mean on the original scale.

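### Section 12.3 gives adverse event rates by grade with no stated attribution basis, while Table 2 reports non-serious Grade 1-2 events only if rated at least 'possible' and Grade 3-4 events at any attribution

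*Combined protocol and SAP*

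**What the plan says.** Section 12.3 sets the population ("Adverse event rates will be summarized in all patients who received AGS-003") and the measure ("These rates will be described as the proportion of patients with the event, by grade, and supported with exact 95% confidence intervals"). Neither this section nor the matching synopsis text limits the events by attribution. Section 12.1 caps the denominator: "A maximum of 10 patients will be enrolled in this study".

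Section 10.7 contains Table 2, headed "Guidelines for Routine Adverse Event Reporting for Pilot Studies". The Unrelated and Unlikely rows are blank at Grades 1 and 2 and marked at Grades 3 and 4. The other three rows are marked throughout, for example "Possible X X X X".

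Other sections bear on the same question:

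- Section 10.5.1 defines an AE without regard to drug relationship. Its list of ratings reads "attribution of ‘unrelated’, ‘unlikely’, ‘probable’, or ‘definite", which omits 'possible'; Section 10.6 and Table 2 include it.
- Sections 10.5.2 to 10.5.5 say what goes on the CRF. None of these rules filters by attribution.
- Section 10.8.2 requires all new serious AEs (SAEs) within its window to be reported, whatever the attribution. Section 15.1 puts every SAE on the AE page as well.
- Section 8.5 limits surgical AEs at the End of Study visit to those that are clinically significant.

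**The concern.** A reader of Section 12.3, knowing the AE definition in 10.5.1, would take each grade column as all-cause incidence. Under Table 2 that holds only for the higher grades. For a non-serious Grade 1 or 2 event, counting depends on whether the investigator rates it 'possible' rather than 'unlikely'. The trial is single-arm and unblinded, and nephrectomy offers a ready alternative explanation for symptoms after surgery. There is no control group against which to check that judgement.

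At stake is what the by-grade table means. A Grade 1-2 rate restricted to related events cannot be set beside an all-cause Grade 3-4 rate as if the two differed only in severity. The exact interval does not help, because it expresses sampling error around whatever was counted and not the loss of events left out. The stopping rule in Section 12.4 has its own event definition and is not affected.

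**Working it through.** The plan states no AE rate, so there is no figure to reproduce. The check sets the rules side by side and then illustrates the size.

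**Step 1. What is counted if Table 2 governs the data**

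| Event | Grade 1-2 | Grade 3-4 |
|---|---|---|
| Non-serious, possible or higher | counted (Table 2) | counted (Table 2) |
| Non-serious, unlikely or unrelated | not counted (blank cells) | counted (Table 2) |
| Serious, any attribution | counted (10.8.2, 15.1) | counted |
| Surgical, at End of Study | only if clinically significant (8.5) | only if clinically significant (8.5) |

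The second row is where the bases part. The Grade 1-2 rate is 'at least possibly related, plus SAEs'. The Grade 3-4 rate is all-cause apart from the surgical limit, which should remove few events of that severity.

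**Step 2. Direction**

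Let A be the number of patients with a given Grade 1-2 event of any cause, and R the number of those with at least one such event that is serious or rated possible or higher. Then R ≤ A. The reported rate is R/n and the all-cause rate is A/n. They are equal only if every patient with the event has a qualifying one.

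**Step 3. Illustrative size**

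Assumptions, none taken from the documents: n = 10 patients treated (the enrolment maximum), A = 4, no event serious. The exact (Clopper-Pearson) 95% limits for x of n are:

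- lower = 0.025 quantile of Beta(x, n − x + 1), or 0 if x = 0
- upper = 0.975 quantile of Beta(x + 1, n − x)

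For x = 2 these are Beta(2, 9) and Beta(3, 8), giving 0.025 and 0.556. For x = 4 they are Beta(4, 7) and Beta(5, 6), giving 0.122 and 0.738.

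With A fixed at 4, the reported result over the possible range of R is:

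| R rated at least 'possible' | Reported rate | Exact 95% CI |
|---|---|---|
| 0 | 0% | 0% to 30.8% |
| 1 | 10% | 0.3% to 44.5% |
| 2 | 20% | 2.5% to 55.6% |
| 3 | 30% | 6.7% to 65.2% |
| 4 (all-cause rate) | 40% | 12.2% to 73.8% |

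At R = 2 the reported rate is half the all-cause rate (20% against 40%). At R = 0 the upper limit of 30.8% lies below the all-cause rate of 40%. Which row would apply cannot be told from the documents.

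**The case against.** The strongest reply is that Table 2 is about reporting, not collection. The CRF rules in Section 10.5 carry no attribution filter, AEs are assessed at every visit from Injection Week #1, and no text says that Table 2 decides what enters the analysis. This stands in part: that the table filters the data is an inference. But Table 2 is the only place that says which routine AEs are reported, and nothing says that the remainder reach the Section 12.3 table by another route. The text needs a decision either way.

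A reader might infer from Section 1.6 that the filter falls exactly where this product's safety signal lies, since "most drug-related adverse events (AEs) have been mild to moderate injection site reactions". The documents do not support that. The sentence describes drug-related events. Injection site reactions are expected and would normally be rated possible or higher under Section 10.6, so they pass the filter. What could be lost is an unrecognised low-grade effect put down to another cause. That is a smaller concern.

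A reader might also infer that the low-grade rates are simply wrong, or cannot be compared with other studies. They are too low only as a measure of all-cause incidence, and only when some events fall below 'possible'; Section 12.3 does not name that target. Recording rules in other studies are not in the documents.

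Finally, Table 2 has no Grade 5 column, but deaths are SAEs under Section 10.8.1 and are captured. Safety is neither the primary nor the secondary objective, and the analysis is descriptive. Both points hold and lower the priority.

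**Conclusion.** The attribution basis of the by-grade AE rates is unstated. On the natural reading of Table 2 it differs between Grades 1-2 and Grades 3-4. The Grade 1-2 rates would then be limited to at-least-possibly-related events plus SAEs, and would understate all-cause incidence whenever some non-serious events are rated unlikely or unrelated. The Grade 3-4 rates would be essentially all-cause, subject to the End of Study limit on surgical AEs.

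This rests on the assumption that Table 2 determines what reaches the database. If all AEs are in fact recorded, the defect reduces to a missing sentence. The size cannot be estimated, because the documents give neither AE rates nor an attribution split; 2/10 against 4/10 is an illustration only. Priority is low to moderate.

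**What to change.** 1. State in Section 10.7 that AEs of every grade and attribution are recorded in the eCRF, so that Table 2 governs onward reporting only.
2. In Section 12.3 and the synopsis, present two rates for each event and grade, all-cause and at-least-possibly-related, each with its exact 95% interval. Note the End of Study limit on surgical AEs as a footnote.
3. If the Table 2 filter is kept for the database, label the Grade 1-2 rates 'at least possibly related (plus SAEs)' and do not set them beside the Grade 3-4 rates without that label.
4. Add 'possible' to the list in Section 10.5.1. This is a clerical alignment with Section 10.6 and Table 2.

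The cost is a few more low-grade entries for at most 10 patients, one extra set of columns and a few words of text. The recording decision is best made before data entry, since low-grade events left out of the eCRF are hard to recover later.

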12.5 Interim Analysis and Criteria for Early Termination of the Study

No explicit interim analyses are planned for this study, given the low stage and slow growth rate of this type of cancer.

13 CORRELATIVE DATA ANALYSIS

Immune parameters will be assessed to demonstrate the effect of AGS-003 on the immune system. Immune effector cell populations will be assessed in a very detailed fashion and will focus on those populations that were found to be of interest in previous studies with AGS-003. Therefore, this study will analyze CD8⁺CD28⁺ T cells (REHA). In addition, this study will analyze T-regulatory cells (CD4⁺CD25⁺FoxP3⁺) and myeloid derived suppressor cells (MDSC) using multicolor flow cytometry. These cell populations will be assessed in peripheral blood specimens as well as in tumor lysates. The serum cytokine microenvironment will be assessed using multiplex Th1/Th2 cytokine ELISA (this will include IL-12 and IFN- γ). If perinephric lymph nodes are removed as standard of care during the kidney surgery, these will be procured and analyzed in a similar fashion. Autologous T cells will be incubated with irradiated autologous tumor cells and T cell proliferation will be measured in IFN- γ ELISPOT assays.

After appropriate tumor tissue has been procured to assure pathologic diagnosis, tumors will be processed into tumor lysates. These lysates will be analyzed using flow cytometry as described above. The tumor infiltrating immune cell populations and tumor cytokine microenvironment will be assessed using standard double-staining immunohistochemistry. These results will be compared to a historical control tissue microarray (TMA) that contains 264 RCC specimens.

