2 RATIONALE

Dendritic cells (DC) are the most potent cells in initiating antigen-specific T cell responses. In particular, they are key players in the initiation of so-called cross presentation. Cross presentation is crucial for the induction of both CD8 cytotoxic T cells and CD4 memory T cells to initiate a memory immune response. The clinical and immunologic potential of an autologous DC immunotherapy was demonstrated in a recent Phase II trial (11). Patients with metastatic kidney cancer received an autologous, tumor-lysate pulsed DC vaccine and showed a median progression free survival (PFS) of 8 months. The median OS has not been reached. Nine objective responses were noted (50%; 95% CI 22%-66%), which included complete responses in 2 patients (19 and 24 months) and 7 partial responses (3-9 months). This trial demonstrated that an autologous DC vaccine can be prepared in a consistent, high-quality fashion (11). Autologous tumor lysate provides a large number of target antigens, but it requires a large volume of tumor tissue. Of particular importance, tumor specimen obtained from reduced quantity of starting tumor tissue, such as from a core needle biopsy procedure, should routinely provide sufficient total tumor RNA to initiate the RNA amplification process, making available ample source material for dendritic cell transfection. AGS-003 combines the most up-to-date DC vaccine technology with the option of targeting a plethora of autologous, tumor-specific target antigens. The data on the clinical efficacy of AGS-003 is becoming increasingly apparent, however, the direct anti-tumor mechanism of action is as of yet undefined. The proposed research study will analyze this mechanism of action. In addition, this neoadjuvant concept of preoperative AGS-003 immunotherapy will lead to better understanding of the role of neoadjuvant immunotherapy

as a means to potentially facilitate tumor resections and may even provide the option of “downsizing” a kidney tumor and change the surgical approach from radical to partial nephrectomy, thus providing significant preservation of precious renal function. If this proposed study demonstrates the expected systemic and intratumoral immune responses, it will lead to the design of a larger Phase II study.

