3 OBJECTIVES

3.1 Primary Objective

- To assess the immune-modulatory systemic and intratumoral effects of AGS-003 as neoadjuvant treatment in patients with localized renal cell carcinoma.

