9.3 Nephrectomy

Fresh tissue will be obtained from the surgical specimen to evaluate the effect of AGS-003 treatment. Samples to be taken are primarily tumor tissue, but may also include normal kidney, adrenal gland, lymph nodes, and /or surrounding tissues as included in the resection. The minimum amount needed is 1g and optimum is 10 grams but additional amounts will be accepted if not required for other institutional research.

The fresh tissue will be sent to [name] laboratory for processing:

Buffalo Life Sciences Complex (BLSC)
Center for Genetics and Pharmacology (CGP)
Laboratory location: L5-141
Lab [contact]

Lab contacts:

[name] [name] PhD-Lab Manager
[name], Assistant Professor, office number: [contact]
[name] [contact]
[name] office number: [contact]
[name] [contact]

For historical comparison, the RCC TMA in existence will be used.

Note: All investigator or analyzing research laboratories housing research samples need to maintain current **Temperature Logs** and study-specific **Sample Tracking and Shipping Logs**. The Principal Investigator/Laboratory Manager **must** ensure that the stated lab(s) have a process in place to document the receipt/processing/storage/shipping of study-related samples/specimens. This is required for both observational and interventional clinical studies collecting clinical samples.

Nephrectomy tissue will also be sent to Argos. Kit for tissue will be provided for each patient by Argos. Sample will be sent to CRS Lab Path Team for processing and shipping. Please see Argos Tumor Worksheet

Tumor Specimen Collection Guidelines for Argos

1 The tumor specimen biopsied must represent viable, non-necrotic tissue that is at least 70% tumor

2 Prepare tumor specimen by completing four (4) biopsy passes for each vial of RNA preservative using 16 gauge or 18 gauge biopsy needles.

NOTE: DO NOT place the specimen in formalin or any other fixative.

NOTE: DO NOT use absorbent material while preparing the tumor specimen.

3 Place the tumor specimen into the RNA preservative vial(s), cap, and gently swirl to separate specimen pieces and adequately immerse specimen pieces in preservative.

NOTE: Only use RNA preservative vials provided with this kit.

4 The tumor specimen should be shipped at room temperature the same day as collection. If the shipment cannot go out the same day as collection, the sealed kit with the tumor specimen in it must be stored in a 2-8° C refrigerator until ready for shipment.

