9.4 Pathology

9.4.1 Pre-Treatment Formalin-Fixed Paraffin Embedded (FPPE) Biopsy Samples

The following sections of tissue from the most recent (Screening) renal cell tissue biopsy (neoplastic) that exists in the Paraffin Archive in the Department of Pathology will be collected:

- Ten (10) unstained sections cut at 5 microns on plus glass slides.

The study coordinator or designee will be responsible for entering the order into the EMR using the standard format for all clinical trial pathology requirements.

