9.4.2 Post-Treatment Resection Formalin-Fixed Paraffin Embedded (FPPE) Samples

The following sections of tissue from the end of treatment nephrectomy (primarily tumor tissue, but may also include normal kidney, adrenal gland, lymph nodes, and /or surrounding tissues) that exists in the Paraffin Archive in the Department of Pathology will be collected:

- Ten (10) unstained sections cut at 5 microns on plus glass slides.

The study coordinator or designee will be responsible for entering the order into the EMR using the standard format for all clinical trial pathology requirements.

Once the samples have been processed by the Pathology Department at RPCI, they will be sent to [name] laboratory:

Buffalo Life Science Complex (BLSC)
Center for Genetics and Pharmacology (CGP)
Laboratory location: L5-141
Lab [contact]

Lab Contacts:

[name]

[name], Assistant Professor, office number: [contact]

[name] [contact]

[name] office number: [contact]

[name] [contact]

Slides will be shipped by the investigator to Adaptive Biotechnologies, Seattle Washington, for analysis.

Note: All investigator or analyzing research laboratories housing research samples need to maintain current **Temperature Logs** and study-specific **Sample Tracking and Shipping Logs**. The Principal Investigator/Laboratory Manager **must** ensure that the stated lab(s) have a process in place to document the receipt/processing/storage/shipping of study-related samples/specimens. This is required for both observational and interventional clinical studies collecting clinical samples.

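### The only comparator named for tumor results is a historical tissue microarray, and the paired test of Section 12.1 is not linked to the biopsy and nephrectomy sections that are collected

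*Combined protocol and SAP*

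**What the plan says.** The primary objective in Section 3.1 is "To assess the immune-modulatory systemic and intratumoral effects of AGS-003 as neoadjuvant treatment in patients with localized renal cell carcinoma". Section 2 attaches a decision to it: "If this proposed study demonstrates the expected systemic and intratumoral immune responses, it will lead to the design of a larger Phase II study".

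Two places name a comparator for tumor results, and both name the same archive. Section 9.3 says "For historical comparison, the RCC TMA in existence will be used", and Section 13 says "These results will be compared to a historical control tissue microarray (TMA) that contains 264 RCC specimens". The documents give the number of specimens, the tumor type and the fact that the array already exists. They do not give stage, histology, era or staining, or how the comparison will be made.

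Section 13 does name tissue readouts. CD8+CD28+ T cells, regulatory T cells and myeloid-derived suppressor cells are measured by flow cytometry in tumor lysates, and infiltrating cells and the cytokine environment by double-staining immunohistochemistry (IHC).

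Section 9.4.1 collects ten unstained sections from the screening biopsy. Section 9.4.2 collects ten more, described as "sections of tissue from the end of treatment nephrectomy". On their use, Section 9.4.2 adds only that "Slides will be shipped by the investigator" to an outside laboratory for analysis.

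The mixed model in Section 12 has a three-level time factor, and the synopsis describes three blood draws. Section 12.1 offers a permutation paired t-test for an immune marker at two time points, and Section 12.2 includes patients measured at two or more time points. Neither mentions tissue.

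**The concern.** Tumor tissue is available before and after treatment from the same patient, but the plan states no contrast between the two. For IHC it names neither the marker, nor the within-patient contrast, nor the test. What it does name is a comparison of at most 10 treated patients, all below pT2, N0 and M0, with 264 archived specimens that may differ in stage, histology, era and staining. If the two groups differ in any of these, the comparison can show an apparent intratumoral effect, or hide one, whatever the drug does. Section 2 makes the expected intratumoral response part of the case for a larger Phase II study, so an artifact here could influence that decision.

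**Working it through.** **Which comparison fits which data.** Blood has three time points, which match the three-level time factor. Tumor has two (screening biopsy, nephrectomy), which match the paired test in Section 12.1. No sentence makes the second match.

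**Inputs.** Maximum 10 patients, log-scale mean 4.38 and SD 0.68, detectable mean 5.08, within-patient correlation 0.50, two-sided 0.05 (all Section 12.1); 264 array specimens (Section 13). Assumptions: the generic SD and correlation apply to tissue, and the array comparison is a two-sample t-test (the plan says only that results are compared).

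**The plan's own figure.** Shift = 5.08 − 4.38 = 0.70. SD of a difference = 0.68 × √(2 × (1 − 0.50)) = 0.68. SE = 0.68/√10 = 0.215. Noncentral t power is 0.825, against the stated 80%. A 0.70 log shift is a ratio of exp(0.70) = 2.01. That does not match the 20% increase stated in the same section, but this is a separate matter.

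**Exposure of the array comparison when the drug does nothing.** SE = 0.68 × √(1/10 + 1/264) = 0.219, with 272 df. For an assumed fold difference f between trial patients and array, the noncentrality is ln(f)/0.219.

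| Assumed difference f | ln f | Noncentrality | Significant in that direction |
|---|---|---|---|
| 1.25 | 0.223 | 1.02 | 17% |
| 1.5 | 0.405 | 1.85 | 45% |
| 2 | 0.693 | 3.16 | 88% |

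With no difference the figure is 2.5% in each direction. The fold differences are assumptions; the documents give nothing to bound them.

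**Power for the 0.70 shift with 10 patients.** Paired SD = 0.68 × √(2(1 − r)).

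| Correlation r | Paired SD | Paired t power |
|---|---|---|
| 0 | 0.962 | 0.54 |
| 0.3 | 0.805 | 0.69 |
| 0.5 | 0.680 | 0.82 |
| 0.7 | 0.527 | 0.96 |

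An array test that happened to be unbiased would have power 0.89 (noncentrality 0.70/0.219 = 3.20).

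**Fewer pairs.** At r = 0.5, paired t power is 0.71 with 8 pairs and 0.53 with 6. An exact sign-flip permutation test on 5 pairs has smallest two-sided p = 2/32 = 0.0625, so it cannot reach 0.05. On 6 pairs the smallest is 2/64 = 0.031, reached only if all six changes share a sign. Power is then Φ(0.70/0.68)^6 + (1 − Φ(0.70/0.68))^6 = 0.37.

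**Time between the two specimens.** The minimum to dose 3 is 2 days (48 hours to leukapheresis) + 42 days (6 weeks of manufacture, assumed to start at leukapheresis) + 10 to 14 days (two weekly intervals, with or without the early window) = 54 to 58 days, about 8 weeks. Participation is about 6 months from consent (Section 4.2), and the last visit is about one month after nephrectomy (Section 8.5). That implies roughly 5 months at most from consent to nephrectomy.

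**The case against.** The strongest reply is that a paired tissue analysis is already the natural reading. Section 12 opens with the intratumoral objective, Section 12.1 does not restrict its paired test to blood, Section 12.2 admits anyone with two measurements, and Section 9.4 labels the specimens pre- and post-treatment. The array could be only an additional, historical comparison. This stands in part: such an analysis may have been intended, and nothing rules it out. But it is not stated, and the one tumor comparison that is stated is the array.

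A reader might infer that the plan has no tissue endpoint at all. Section 13 does not support that, since it names lysate cell populations and IHC targets. The gap is the IHC marker, the contrast and the test.

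A reader might also infer that pairing is more powerful, or that it would show the drug's effect. Neither follows. At correlation 0.50 the paired test has slightly less power than an unbiased array test. The paired change also still includes the effect of the biopsy itself, core-versus-resection sampling and elapsed time. Nor is the elapsed time unlimited: Sections 4.2 and 8.5 imply an approximate ceiling.

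Finally, this is a 10-patient pilot and Section 13 ranks no assay. That argues for a modest change and does not justify leaving the contrast unstated.

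**Conclusion.** The point holds as a gap in specification that is cheap to close. Intratumoral effect is part of the primary objective, the only named tumor comparator is an array without the details needed to judge comparability, and the plan's own paired method is not linked to the paired sections it collects. Under the assumptions shown (log SD 0.68, two-sample t-test, 10 against 264, no drug effect), a 1.25- to 2-fold difference in population or staining produces a significant result in that direction in about 17% to 88% of trials. A within-patient change removes between-patient case mix and, with same-batch staining, the assay difference. The argument rests on which sources of difference each comparison removes, and not on power. In a single-arm trial the paired change is better controlled than the array comparison but does not by itself establish attribution to AGS-003.

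**What to change.** In Sections 12 and 13:

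- Make the within-patient change from screening biopsy to nephrectomy the main comparison for the IHC tumor results, using the permutation paired t-test of Section 12.1 in patients with both specimens.
- Name the IHC marker or markers, and stain and score each pair in the same batch.
- Report the number of complete pairs. With fewer than 6, show individual changes without a test.
- Describe the array and keep it as descriptive context, limited to specimens below pT2 if stage is recorded.
- Report lysate flow cytometry descriptively, because no pre-treatment counterpart is stated.
- Confirm that enough sections remain for IHC after the outside shipment.

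The cost is SAP wording, same-batch staining and a decision on dividing the sections between IHC and the outside laboratory. No extra biopsy or visit is needed.

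Pairs may be missing. The collection guidelines for material going to the manufacturer say "DO NOT place the specimen in formalin or any other fixative", so those cores cannot also supply paraffin sections. Patients whose tumor RNA fails are removed (Section 6.1). The report should also state that biopsy effect, sampling difference and elapsed time remain in the paired change.
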